7.6. Pharmacodynamic parameters

Missing data for the pharmacodynamic parameters will be treated as such and no imputed values will be derived.

8. STATISTICAL METHODOLOGY AND STATISTICAL ANALYSES

8.1. Statistical Methods

Whilst every effort has been made to pre-specify all analyses in this statistical analysis plan, if additional exploratory analyses are found to be necessary, the analyses and the reasons for them will be detailed in the clinical study report (CSR).

8.1.1. Analysis for Time-to-Event Data

Time-to-event endpoints will be summarized using the Kaplan-Meier (KM) method [3] and displayed graphically when appropriate. Median event times and 2-sided 95% confidence intervals for each time-to-event endpoint [2] will be provided. KM analysis will only be performed if the number of events is no less than 5.

8.1.2. Analysis for Binary Data

Point estimates of binary endpoints will be provided for each treatment arm along with the corresponding 2-sided 95% confidence intervals using an exact method [1].

8.1.3. Analysis for Continuous Data

Descriptive statistics, such as the mean, standard deviation, coefficient of variation, median, minimum, and maximum values will be provided for continuous endpoints. Linear or non-linear models may be employed to analyze the continuous data.

8.2. Statistical Analyses

In general, all data will be summarized by arm and sub-cohort, unless otherwise specified.

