**Table 2 Disease Control Rate – Third Line** 

	Monotherapy (Historical)	Combination * (Historical)	Combination with BBI608 (Expected)
Cetuximab	30-40% 	~ 63% 	60% or more
Panitumumab	30-40% 	~ 68% 	60% or more
Capecitabine	~ 15% 	~ 45% 	60% or more

\* Cetuximab + Irinotecan
Panitumumab + Irinotecan
Capecitabine + Mitomycin C

For the Cetuximab and Panitumumab combination cohorts, if the disease control rate in stage 1 reaches 3 of 8 or above, additional patients will be enrolled into the stage 2 cohort. For the

Capecitabine combination cohort, if the disease control rate in stage 1 reaches 2 of 6 or above, additional patients will be enrolled into the stage 2 cohort.

To evaluate the tolerability of BBI608, patients from each arm will be assigned to one of 4 subcohorts (with 6 patients in each sub-cohort IA, IB, IIA, IIB). The evaluation of tolerability will be done at select centers for the study arm that is continuing patient accrual and in which a total of 50 evaluable patients has not been reached. For each combination arm, patients assigned to sub-cohorts IA and IB will receive BBI608 at 240 mg po twice daily (480 mg total daily dose) starting on day 1 of cycle 1. Intra-patient dose escalation of BBI608 to 480 mg po twice daily (960 mg total daily dose) is allowed as tolerated. Patients assigned to sub-cohorts IIA and IIB will receive BBI608 at 480 mg po twice daily (960 mg total daily dose) starting on day 1 of cycle 1. In case of toxicity, dose adjustment of BBI608 is permitted, as recommended in dose modification guidelines. Additionally, patients assigned to sub-cohorts IA and IIA will receive prophylactic anti-diarrheal treatment starting the day prior to day 1 of cycle 1. Patients assigned to sub-cohorts IB and IIB will anti-diarrheal treatment on an as needed basis starting with development of diarrhea above baseline. For each combination regimen, patients will be sequentially assigned to each of the 4 sub-cohorts in the following order until 6 patients are accrued on each of the sub-cohorts: IA, IB, IIA, and IIB. If required, up to additional 20 patients may be assigned to selected sub-cohorts to validate the observations in initial 6 patients.

Table 3 Tolerability Analysis of BBI6	U8
---------------------------------------	----

Sub-cohort	BBI608 Starting Dose Level	Anti-diarrheal Administration

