2.1. Study Design

This is an open label, multi-center, Phase II study of napabucasin (BBI608) administered in combination with either cetuximab, or panitumumab, or capecitabine to patients with advanced colorectal cancer. The study is designed to explore the safety, tolerability, preliminary anti-tumor activity and pharmacokinetics of napabucasin when administered in combination with each one of the above regimens.

Six patients would be initially enrolled in each combination arm at a napabucasin dose level of 500 mg BID (1000 mg total daily using 50 mg capsules) before protocol amendment 2 or 480 mg twice daily (960 mg total daily dose) using 80 mg capsules after protocol amendment 2. If ≤ 1 out of 6 patients had an observable dose limiting toxicity (DLT) in the combination regimen, then that arm of the study would continue to enroll patients at 500 mg BID (1000 mg total daily) using 50 mg capsules or 480 mg BID (960 mg total daily) using 80 mg capsules following a Simon 2-stage design. If a DLT occurred in ≥ 2 of the 6 patients in a combination arm, then that arm of the study would be closed and no further patients would be enrolled. A given arm of napabucasin in combination with cetuximab, or panitumumab, or capecitabine would continue to enroll patients if no more than 1 out of 6 patients in the combination arm had an observable DLT.

The number of colorectal cancer patients enrolled would be based on a two-stage Simon design and is presented in Section 4.1 of the protocol amendment 2 [5]. If any of the three arms reach a disease control rate (DCR) of 60% or higher at the end of the Simon Stage 2 portion of the study, a one-time option to expand accrual to a total sample size of up to 50 patients may be implemented for each arm.

To evaluate the tolerability of napabucasin, patients from each arm would be assigned to one of 4 sub-cohorts (with 6 patients in each sub-cohort: IA, IB, IIA, IIB) from protocol amendment 2. The evaluation of tolerability would be done at selected centers for the study arm that was continuing patient accrual and in which a total of 50 evaluable patients had not been reached. For each

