combination arm, patients assigned to sub-cohorts IA and IB would receive napabucasin at 240 mg twice daily (480 mg total daily dose) starting on Day 1 of Cycle 1. Intra-patient dose escalation of napabucasin to 480 mg twice daily (960 mg total daily dose) was allowed for patients in these cohorts as tolerated. Patients assigned to sub-cohorts IIA and IIB would receive napabucasin at 480 mg twice daily (960 mg total daily dose) starting on Day 1 of Cycle 1. In the event of toxicity, dose adjustment of napabucasin was permitted, as recommended in dose modification guidelines. Additionally, patients assigned to sub-cohorts IA and IIA would receive prophylactic anti-diarrheal treatment starting the day prior to Day 1 of Cycle 1. Patients assigned to sub-cohorts IB and IIB would receive anti-diarrheal treatment on an as-needed basis starting with development of diarrhea (ie, any occurrence greater than the patient's baseline). For each combination regimen, patients would be sequentially assigned to each of the 4 sub-cohorts in the following order until 6 patients were accrued in each of the sub-cohorts: IA, IB, IIA, and IIB. If required, up to an additional 20 patients might be assigned to selected sub-cohorts to validate the observations in the initial 6 patients.

Sub-cohort	Napabucasin Starting Dose Level	Anti-diarrheal Administration*
IA	240 mg bid (480 total daily dose) ¹	Prophylactic
IB	240 mg bid (480 total daily dose) ¹	As needed
IIA	480 mg bid (960 total daily dose) ²	Prophylactic
IIB	480 mg bid (960 total daily dose) ²	As needed

Table 1 Tolerability Analysis of Napabucasin

¹Intra-patient dose escalation of napabucasin to 480 mg po twice daily (960 mg total daily dose) is allowed as tolerated. ²In case of toxicity, dose adjustment of napabucasin is permitted.

*See protocol amendment 2 [5] section 7.1.4 for details

A study cycle would consist of 28 days of daily administration of napabucasin in combination with cetuximab or panitumumab, or capecitabine. Cycles would continue until unacceptable toxicity, disease progression (clinical or radiological) or another discontinuation criterion is met. Pharmacokinetic (PK) assessments would be performed on the first 6 patients enrolled in each combination arm. Pharmacodynamic assessments would be performed in patients with readily accessible tumor tissue through an optional tumor biopsy. Evaluation of anti-tumor activity would be performed at 8-week intervals per RECIST 1.1 while patients remain on study.

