2.1.2. Secondary Objectives

The secondary objectives of this study are as follows:

- To determine the pharmacokinetic profile of napabucasin and cetuximab, or panitumumab, or capecitabine when administered in combination.
- To determine the pharmacodynamics (biomarkers) of napabucasin.
- To evaluate tolerability of two dosing regimens of napabucasin by comparing administration of napabucasin at a 240 mg twice daily starting dose and escalating to 480 mg twice daily after Cycle 1 versus administration of napabucasin at a 480 mg twice daily starting dose with dose adjustment permitted.
- To evaluate tolerability of napabucasin by comparing prophylactic administration of anti-diarrheal medication versus as-needed administration of anti-diarrheal medication. The tolerability will be assessed using the adverse event profile and achieved dose intensity.

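### The sub-cohorts cross starting dose with anti-diarrheal strategy, but the SAP specifies no marginal contrast for either exploratory tolerability objective

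*SAP*

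**What the plan says.** SAP 2.1.2 lists two tolerability objectives worded as comparisons. The first begins "To evaluate tolerability of two dosing regimens of napabucasin by comparing administration of napabucasin at a 240 mg twice daily starting dose" and sets this against a 480 mg twice-daily start. The second is "To evaluate tolerability of napabucasin by comparing prophylactic administration of anti-diarrheal medication versus as-needed administration of anti-diarrheal medication". On measurement it adds: "The tolerability will be assessed using the adverse event profile and achieved dose intensity". Protocol 2.2 has the same objectives.

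SAP 2.1 and Protocol 4.1 describe the layout. IA and IB start at 240 mg twice daily, and IIA and IIB at 480 mg twice daily. IA and IIA receive prophylactic anti-diarrheal medication, and IB and IIB receive it as needed. The planned size in each combination arm is "with 6 patients in each sub-cohort: IA, IB, IIA, IIB", with a possible extension: "If required, up to an additional 20 patients might be assigned to selected sub-cohorts to validate the observations in the initial 6 patients".

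The reporting rule in SAP 8.2 is "In general, all data will be summarized by arm and sub-cohort, unless otherwise specified". Protocol 10.8 also analyzes each sub-cohort separately, for diarrhea days and compliance over two cycles. It calls these questions exploratory, yet quotes power for a comparison of two groups.

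**The concern.** Each objective is a question about one factor. In a 2x2 layout the natural estimate is the marginal difference, which uses every sub-cohort patient for both questions. The SAP sections on exposure and compliance (8.2.1) and on adverse events and diarrhea days (8.2.4.1) give summaries only. The interval in SAP 8.1.2 for binary endpoints is placed around each rate, not around a difference.

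If the plan is followed as written, neither objective receives an estimate. The reader has to compare small cells by eye or build the margins without a stated method, and a choice of contrast made after the data are seen is open to selection.

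**Working it through.** **1. The plan's own power figures.** Inputs from Protocol 10.8: 20 patients, two-sided pooled Z test, type I error 0.15 (z = 1.440); control rates 70% (compliance) and 30% (diarrhea); differences of 20 and 25 points; stated power 80% and 57%.

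Power = Φ{[|d| − z·√(2·p̄(1−p̄)/n)] / √[(p1(1−p1) + p2(1−p2))/n]}, with n per group.

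- Compliance, 70% vs 90%, n = 20: (0.20 − 1.440 × 0.1265)/0.1225 = 0.146, so power is 55.8%. The stated 80% is not reproduced; it needs about 40 per group (79.5%).
- Diarrhea, n = 20: an increase from 30% to 55% gives 56.6%, which matches the stated 57%. A reduction from 30% to 5% gives 75.1%.

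The documents do not settle which group size or direction lies behind the two figures. The protocol's rates are used below only as a common yardstick.

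**2. Patients behind each comparison.** The plan has 6 per cell, 4 cells per arm and 3 arms.

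- Two single cells in one arm: 6 vs 6.
- One arm's margin: 6 + 6 = 12 vs 12.
- Margin over three arms: 3 × 12 = 36 vs 36, or 72 patients in all.

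**3. Precision for 70% vs 90%.** SE = √[(0.7×0.3 + 0.9×0.1)/n] = √(0.30/n); half-width = 1.96 × SE. Power uses the formula in step 1.

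| Comparison | n per side | SE | 95% half-width | Power at 0.15 |
|---|---|---|---|---|
| Two cells, one arm | 6 | 0.224 | 44 points | 28% |
| One arm's margin | 12 | 0.158 | 31 points | 41% |
| Margin over three arms | 36 | 0.091 | 18 points | 76% |

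The power column shows information only, since SAP 4.1 plans no test. The last row also takes the two rates to be the same in every arm.

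**4. Extended cells.** Suppose one cell takes all 20 extra patients (26) and is set against an unextended cell of 6. The half-width is then 1.96 × √(0.21/26 + 0.09/6) = 30 points if the 70% cell is the larger one, and 1.96 × √(0.21/6 + 0.09/26) = 38 points if the 90% cell is. Extension helps, but it defines no contrast.

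**5. Dose-intensity denominator.** SAP 8.2.1 gives the intended napabucasin dose as 500 mg twice daily, yet also fixes the intended level at the start of treatment. The sub-cohorts start at 240 or 480 mg twice daily. On a 500 mg denominator, a patient who stays on the assigned starting dose scores 240/500 = 48% or 480/500 = 96%. A starting-dose contrast of relative dose intensity would then show a 48-point gap by construction.

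**The case against.** The case for leaving the SAP alone is that this work is exploratory by declaration. Protocol 10.8 calls the questions hypothesis-generating and has extension decided on clinical grounds, Protocol 10.1 plans no formal analysis, and SAP 4.1 has no hypothesis testing. The SAP also leaves openings. Its reporting rule applies in general unless otherwise specified. Daily compliance is reported by an undefined dose-level cohort, which might mean the dose margin. Models may be used for continuous data, and further exploratory analyses are allowed if the study report explains them.

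Much of this stands, and it limits the point. A reader might infer that the SAP reports only cells of six. It does not, because six is the initial size and selected cells can grow. A reader might also infer that half the data are ignored for each question. Nothing is dropped: every cell is tabulated, and counts can be added across cells. Nor is a required test missing, because none is planned.

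What does not stand is that the openings fill the gap. None names a factor, endpoint or contrast, and the dose-level grouping cannot serve the anti-diarrheal objective. Exploratory status removes the need for a test but not for an estimate that matches the stated objective.

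Two further objections concern the margins themselves, and both are fair. Allocation is sequential in the order IA, IB, IIA, IIB (Protocol 4.1) and non-randomized (Protocol 11.2). If the cells fill one after another, all 240 mg starts precede all 480 mg starts within an arm, so starting dose cannot be separated from calendar time and a narrow pooled interval would mislead. If patients rotate through the cells, the problem is much smaller; the wording allows either reading. The 36 vs 36 case is also a ceiling. It needs 72 sub-cohort patients, whereas Protocol 3.3 expects about 60 to 80 in the whole study, and the sub-cohorts run only at select centers in arms still accruing.

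**Conclusion.** The point holds in a limited form. The SAP specifies no marginal contrast, and no difference with an interval, for either exploratory tolerability objective, although the layout supports both. This is an unspecified estimate rather than lost data or an omitted test, and it should be corrected.

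Using the margins cuts the 95% half-width from about 44 points to 31 within one arm, and to 18 at best over three. These figures rest on the protocol's binary simplification at 70% and 90% and on a normal approximation that is poor at 6 per side. They do not carry over directly to mean compliance, dose intensity or diarrhea days, whose variability the documents do not give. The gain in precision also assumes no large interaction between the two factors and does nothing about confounding with calendar time or center.

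**What to change.** Add to SAP 8.2, for compliance, actual dose intensity, diarrhea days and treatment-emergent adverse events:

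- starting dose: the estimated difference IA+IB versus IIA+IIB;
- anti-diarrheal strategy: the estimated difference IA+IIA versus IB+IIB;
- each stratified or adjusted for combination arm and for the other factor, with a 95% confidence interval, labelled descriptive and exploratory.

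Keep the arm-by-sub-cohort tables so that interaction can be checked. State next to the results that allocation was sequential and non-randomized, that the contrasts (starting dose above all) may be confounded with calendar time and center, and in what order the cells actually filled.

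Two things need reconciling first. The passages on intended napabucasin dose must agree before relative dose intensity is compared. The SAP's compliance formula also divides by intended dose, so the same applies to it, whereas Protocol 10.8 counts capsules per dose level. The diarrhea measure must also agree: Protocol 10.8 counts Grade II/III days in the first two cycles, while SAP 8.2.4.1 counts Grade II or above with no two-cycle window.

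The cost is modest. No new data are needed, but stratified or adjusted intervals for four measures take some programming and a short methods paragraph.

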8.2.1. Standard Analysis

Study Conduct and Patient Disposition

Patient disposition includes the number and percentage of patients for the following categories: patients in each of the study populations, patients discontinued from the study, and primary reason to discontinue from the study. The summary will be based on the FAS.

Demographic and Baseline Characteristics

Baseline characteristics such as demographics, prior medication, medical history, Eastern Cooperative Oncology Group (ECOG) performance status, and primary diagnosis will be tabulated for the safety set and listed for the FAS.

- Demographics: Demographics will be summarized in a descriptive fashion. Baseline demographic data to be evaluated will include age, sex, race, height, weight, and other parameters as appropriate. Patient enrollment by region and country may be summarized.
- Baseline disease characteristics: ECOG performance status, stage at study entry, and K-RAS mutation status.

Prior and Concomitant Medications

Prior and concomitant medications will be coded to ATC (Anatomical Therapeutic Chemical) classification and Drug Name using WHO Drug Dictionary (WHO-DD) (March 2015).

Medications that start and stop prior to the date of first treatment administration (either napabucasin or backbone chemotherapy, whichever is administered first) will be classified as 'prior' medications. If a medication starts on or after the date of first treatment administration, then the medication will be classified as 'concomitant'. If a medication starts before the date of first treatment administration, then the medication will be categorized as both a 'prior' and 'concomitant' medication.

Summaries of prior and concomitant medications will be provided by level 3 ATC classification and preferred term using frequencies and percentages for the safety analysis set. Additional summary of concomitant medication will be provided by preferred name base and drug class.

Prior Cancer Treatment

Prior cancer treatment included surgery plus radiotherapy and hormone /biologic/ chemotherapy /other treatments, where the former will be coded using the Medical Dictionary for Regulatory Activities (MedDRA[®]) version 18.0 and the latter will be coded using WHO Drug.

Prior cancer treatment may be summarized by System Organ Class (SOC) and Preferred Term (PT) as appropriate for each patient in the safety analysis set.

Medical History

Medical history will be coded by SOC and PT using the MedDRA version 18.0 prior to the analysis. Medical history will be summarized by SOC and PT using the number and percentage of patients

for the safety analysis set.

Duration of Overall Survival Follow-up

The duration of overall survival (OS) follow-up is defined as time from the date of first treatment to death or the last known alive visit. The median follow-up time for OS and the corresponding 95% confidence interval (using the method of Brookmeyer and Crowley, 1982 with the log-log transformation) will be summarized using the reverse Kaplan-Meier (KM) method for the safety set. The analysis involves the event and censoring rules to be switched (ie, the patients who die become 'censored', and the censored patients are treated as the 'event').

Summaries of the number and percentage of patients who have died, those still in survival followup, those lost to follow-up, and those who have withdrawn consent will be also provided.

Extent of Exposure

Exposure may be summarized as dose received (cumulative dose or actual dose intensity) or as dose received relative to the intended dose (relative dose [RD], or relative dose intensity [RDI]), or both.

The information that will be summarized depends on how the study drug is dosed (eg, infusion cyclical, oral daily, oral cyclical).

In what follows, "time unit" can be weeks or days.

Actual treatment duration = actual end of treatment date – date of first dose of study drug + 1, where

- For napabucasin and Capecitabine, the actual end of treatment date is the last dosing date
- For cyclic combination drugs in Arms A and B, actual end of treatment date = last dose of cyclic dosing + interval 1, where interval = 7 for Arm A and interval =14 for Arm B.

Cumulative dose in a cycle or overall is the sum of the actual doses received in a cycle or overall, respectively.

Actual Dose Intensity [DI]

- By cycle actual DI (*dose unit/week*) = [cumulative dose in the cycle]/ [actual cycle duration in *weeks*]
- Overall actual DI (*dose unit/week*) = [overall cumulative dose] / [actual treatment duration in *weeks*]
- Note that actual DI for cyclical dosing is calculated based on actual cycle duration in all but the last cycle where it is fixed at the intended duration.

Relative Dose Intensity (RDI): The basic intent is to evaluate dose per *time unit* factoring in dose reductions, interruptions, or delays.

Relative dose intensity (RDI) by cycle and overall

- Intended DI (*dose unit/time unit*) = [intended cumulative dose per cycle] / [intended number of *time units* in a cycle]
- By cycle RDI (%) = $100 \times [by cycle actual DI] / [intended DI]$
- \circ Overall RDI (%) = 100 × [overall actual DI] / [intended DI]

Note the intended dose level is fixed at the start of treatment rather than the start of a cycle

- One exception is for Cetuximab. For Cetuximab, dose level is permitted to change from 400 mg/m^2 on day 5 in cycle 1 to 250 mg/m² for each subsequent infusion. If dose level decreases for Cetuximab 4-7 days after first dose date, then updated dose level is the new intended dose level for Cetuximab.
- Second exception is for all backbone therapies. All backbone therapies incorporate BSA or weight to calculate each dose. Panitumumab incorporates weight to calculate each dose-all other therapies incorporate BSA. Therefore, the BSA to be used for calculating each dose of the backbone therapies will be using the Mosteller method (see below) based on the last available weight and height prior to each infusion. For Panitumumab, the last available weight prior to each infusion will be used for calculating each dose.
- $BSA [m^2] = ((Height [cm] \times Weight [kg])/3600) \times 0.5$
- Calculated doses will be rounded to the nearest integer
- Cumulative dose, actual dose intensity and relative dose intensity will remain missing if they cannot be derived due to missing weight, or BSA. Height from the most recent earlier visit can be used if height is missing.

The intended cumulative dose of napabucasin per cycle is calculated by (intended dose level per day) \times (intended cycle duration in days)

• Intended dose level per day for napabucasin is 500mg po BID

Dose unit of napabucasin is mg, dose unit of other combination drugs (except Panitumumab) is mg/m^2 , dose unit of Panitumumab is mg/kg.

Treatment compliance

Treatment compliance for napabucasin is defined as follows:

(Cumulative actual total dose / total planned or intended dose) $\times 100 = \%$ compliance

For any IV combination drug (Cetuximab and Panitumumab), compliance will be calculated using the following equation:

(Number of treatments administered / number of treatments that should have been administered) $\times 100 = \%$ compliance

For oral combination drug (Capecitabine), compliance will be calculated using the following equation:

(Cumulative actual total dose / total planned or intended dose) \times 100 = % compliance

Daily treatment compliance will be reported for each patient by dose level cohort.

- The % of days the patient received full daily dose of napabucasin or higher out of actual treatment duration in days.
- The % of days the patient received a non-zero dose of napabucasin out of actual treatment duration in days.
- The % of days the patient received full daily dose of napabucasin or higher out of the first 56 days from treatment start.
- The % of days the patient received a non-zero dose of napabucasin out of the first 56 days from treatment start.

Daily treatment compliance will be grouped according to the following categories: < 60%, $\geq 60\% - < 80\%$, $\geq 80\% - < 90\%$, $\geq 90\%$, and will be summarized for all arms.

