### 4 INVESTIGATIONAL PLAN

# 4.1 Overall Study Design

This is an open-label, multicenter Phase II study of oral BBI608 administered with Cetuximab, or Panitumumab, or Capecitabine to patients with advanced metastatic colorectal cancer. The study is based on a Simon 2-stage design that will examine the safety, tolerability and pharmacokinetics of BBI608 and Cetuximab, or Panitumumab, or Capecitabine, and assess the preliminary anti-tumor activity of BBI608 when administered in combination with Cetuximab, or Panitumumab, or Capecitabine in patients with advanced colorectal cancer.

BBI608 treatment will be at a dose level of 480 mg twice daily (960 mg total daily dose). In each cycle, BBI608 will be taken daily continuously for 4 weeks (28 days). BBI608 will be administered twice daily approximately one hour prior to or two hours after meals with the first dose given in the morning and approximately 12 hours between doses.

For patients receiving Cetuximab therapy, Cetuximab will be administered IV on day 5 of cycle 1 at 400 mg/m² intravenous infusion over 120 minutes as the initial dose, then weekly at 250mg/m² over 60-minutes at subsequent cycles.

For patients receiving Panitumumab therapy, Panitumumab will be administered IV on day 8, and 22 of each 28 day cycle at 6 mg/kg over 60 minutes.

For patients receiving Capecitabine therapy, Capecitabine will be administered orally at 1000 mg/m^2 bid daily on days 8-21 every three weeks.

Cycles will be repeated until progression of disease, unacceptable toxicity, or another discontinuation criterion is met. In the case of toxicity, adjustment is permitted. If administration of Cetuximab, or Panitumumab, or Capecitabine is discontinued due to Cetuximab, or Panitumumab, or Capecitabine-related toxicity, administration of BBI608 will be continued until disease progression if tolerated.

Initially, 6 patients will be enrolled in each combination arm at a dose level of 480 mg twice daily (960 mg total daily dose) BBI608. If  $\leq 1$  out of 6 patients has an observable DLT in the combination regimen, then that arm of the study will continue to enroll patients at 480 mg po twice daily (960 mg total daily dose) of BBI608 following the Simon 2-stage design (see Table 1). If

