## 7.1.3 Cetuximab, Panitumumab, or Capecitabine Administration

- Detailed instructions for the preparation, premedication, and administration of Cetuximab, Panitumumab, or Capecitabine are provided in the Product Labels approved by Health Canada or US FDA.
- Cetuximab will be administered via IV on Days 5, 12, 19 and 26 of a 28 day cycle, about 3 hours after the first daily dose of BBI608. Panitumumab will be administered via IV on Days 8, and 22 of a 28 day cycle, about 3 hours after the first daily dose of BBI608. Capecitabine will be administered orally twice-daily for two weeks out of three weeks. The first dose of Capecitabine should be taken about 3 hours after the first daily dose of BBI608 on day 8 of each 3 week cycle of Capecitabine.

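### SAP 8.2.1 ends capecitabine duration at the last tablet with no allowance for the drug-free week; counted from the first capecitabine dose, full dosing reads 150% to 107% overall relative dose intensity

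*SAP*

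**What the plan says.** On extent of exposure, SAP 8.2.1 defines "Actual treatment duration = actual end of treatment date – date of first dose of study drug + 1". The end date then depends on the drug. "For napabucasin and Capecitabine, the actual end of treatment date is the last dosing date". In the antibody arms a dosing interval is added: "For cyclic combination drugs in Arms A and B, actual end of treatment date = last dose of cyclic dosing + interval", less one day, "where interval = 7 for Arm A and interval =14 for Arm B". (The minus sign before the 1 is lost in the extracted text; I read it as interval minus one.)

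Overall actual DI is the cumulative dose divided by this duration in weeks. Intended DI is the planned dose per cycle divided by the planned length of that cycle, rest included. Overall RDI is 100 times the ratio of the two. A note in the same section says that, for cyclical dosing, the last cycle takes its planned length in place of its actual length. The section also names oral cyclical dosing as one of the dosing types.

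Protocol 4.1 gives capecitabine 1000 mg/m² "bid daily on days 8-21 every three weeks". Protocol 7.1.3 adds that "Capecitabine will be administered orally twice-daily for two weeks out of three weeks", with the first dose "on day 8 of each 3 week cycle of Capecitabine". The free week is therefore days 1-7 of each course and comes before the tablets.

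**The concern.** Capecitabine shares an end-date rule with BBI608, which is taken every day without a break. For a continuous drug, the last dosing date is the natural end of exposure. For a drug taken two weeks in three, the span from first to last tablet over n courses contains only n-1 free weeks, while the intended DI it is compared with assumes n. The ratio is then too high, most of all in patients who stop early.

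The trial studies combinations. A reader of the exposure tables wants to know whether the partner drug was delivered as planned, and the SAP says that RDI is meant to reflect reductions, interruptions and delays. A figure that shows 150% when nobody took more than the planned dose does not serve that purpose, and it cannot be compared with the antibody arms.

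**Working it through.** The documents give no RDI figure, so there is none to reproduce. I applied the SAP formulas to the protocol schedule.

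**Inputs**

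- Daily dose: 2 × 1000 = 2000 mg/m² (Protocol 4.1).
- Dose per course: 14 × 2000 = 28,000 mg/m².
- Intended DI: 28,000 / 3 weeks = 9,333 mg/m²/week.
- Expected treatment period: 4 to 16 weeks (Protocol 4.6). Courses fall on days 8-21, 29-42, 50-63, 71-84 and 92-105, so this covers one to five completed courses.

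**Full dosing, two start dates**

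The last tablet of course n falls on day 21n. From the first capecitabine dose (day 8), duration = 21n - 8 + 1 = 21n - 7 days, or 3n - 1 weeks. Hence RDI = [28,000n / (3n - 1)] / [28,000 / 3] = 3n/(3n - 1). From BBI608 Day 1, duration = 21n days and RDI = 100%.

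| Courses | Days from first capecitabine dose | RDI | Days from Day 1 | RDI |
|---|---|---|---|---|
| 1 | 14 | 150% | 21 | 100% |
| 2 | 35 | 120% | 42 | 100% |
| 3 | 56 | 112.5% | 63 | 100% |
| 4 | 77 | 109.1% | 84 | 100% |
| 5 | 98 | 107.1% | 105 | 100% |

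**Reduced dosing, counted from the first capecitabine dose**

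- 100% then 75% (true 87.5%): 49,000 / 5 weeks = 9,800; 9,800 / 9,333 = 105%.
- Four full courses then 75% (true 95%): 133,000 / 14 weeks = 9,500; 101.8%.
- 100%, 75%, 50% (true 75%): 63,000 / 8 weeks = 7,875; 84.4%.
- Five courses at 75%: 105,000 / 14 weeks = 7,500; 80.4%.

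A constant dose reads 100% or more only if it is at least (3n - 1)/(3n) of the planned dose: 66.7% for one course, 83.3% for two, 93.3% for five.

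**Does a Day 1 start work in Arm B?**

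Panitumumab 6 mg/kg on days 8 and 22 gives 12 mg/kg per 28-day cycle, an intended DI of 3 mg/kg/week. The end date is 22 + 14 - 1 = day 35.

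- From the first panitumumab dose: 35 - 8 + 1 = 28 days; 12 / 4 = 3; RDI 100%.
- From Day 1: 35 days; 12 / 5 = 2.4; RDI 80%.

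The interval rule returns 100% in Arm B only with a drug-specific start, and that is the start under which capecitabine reads 150% to 107%.

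**Last-cycle note**

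If the last capecitabine course is counted at 21 days, duration from its first dose is 21n days and RDI is 100% for every n.

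**The case against.** The strongest reply is that two readings of SAP 8.2.1 already give 100% for capecitabine. First, the term study drug may mean BBI608, as it does in the PFS censoring table of SAP Appendix 1.3. Because the protocol puts the free week before the tablets, a Day 1 start then counts every free week. Second, the last-cycle note may be meant to cover capecitabine, the only oral cyclical drug in the trial, in overall as well as by-cycle DI.

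Both readings are possible, so the SAP cannot be said to yield 150% to 107% without qualification. Neither removes the problem. SAP 6.2 also uses study drug for any of the drugs, and a Day 1 start makes a perfect panitumumab cycle read 80%. The note is about cycle duration, whereas overall DI uses treatment duration, which has its own explicit capecitabine end date. If the note does govern overall DI, it contradicts that line.

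A reader might go further and infer that a Day 1 start also understates cetuximab. The documents do not support this. SAP 8.2.1 allows the lower maintenance dose to become the intended level. Four infusions total 400 + 3 × 250 = 1150 mg/m²; over 32 days this is 251.6 mg/m²/week, or 100.6% of 250. The conflict between start dates is shown for panitumumab, not for cetuximab.

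A reader might also infer that dose reductions in general disappear from view. They do not: the 84.4% and 80.4% above are plainly below 100%, and by-cycle RDI is defined as well.

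**Conclusion.** The capecitabine end-date rule is inconsistent with the intended DI it is divided by, with the rule for the antibody arms, and with the SAP's own last-cycle note. With a drug-specific start, overall RDI for full dosing is overstated by a factor of 3n/(3n - 1), from 150% after one course to 107% after five. Small or late reductions and short exposures can be masked. With a Day 1 start capecitabine is right, but one perfect panitumumab cycle reads 80%. On either start date the stated rule misreports one partner drug, so this is more than a missing detail.

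The figures assume completed courses, no delays, a 21-day capecitabine cycle as the planned cycle, and an interval-minus-one end date in Arm B.

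The consequence is limited. The SAP makes RDI one of several optional exposure summaries, and it is not the primary endpoint. Capecitabine compliance is actual over planned total dose, has no duration term and is unaffected. The correction is worth making, but it does not bear on the main efficacy result.

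**What to change.** In SAP 8.2.1:

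- Define actual treatment duration separately for each drug, from that drug's first dose.
- Remove capecitabine from the line that ends duration at the last dosing date.
- For capecitabine, set duration = (start of last course - first capecitabine dose) + 21 days.
- State that the last-cycle note governs overall DI for capecitabine as well as by-cycle DI.

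Full-dose capecitabine then reads 100% for any number of completed courses, and 100% followed by 75% reads 87.5%.

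The cost is one or two lines of text and the matching programming. Two effects should be disclosed. Reported capecitabine RDI will fall. A patient who stops partway through the last course will read below 100%: seven full-dose days of a single course give 14,000 / 3 weeks = 4,667 mg/m²/week, or 50%.

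The same edit should say how the cetuximab loading dose enters intended DI. With a drug-specific start and 250 mg/m² as the only intended level, one perfect cycle reads 1150 / 4 = 287.5 mg/m²/week, or 115%.
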